### 7.1 INCLUSION CRITERIA

- I 01. Adult patients with a physician diagnosis of asthma for at least 12 months based on the Global Initiative for Asthma (GINA) 2017 Guidelines (1).
- I 02. Patients with existing treatment with medium to high dose ICS ( $\geq 250$  mcg of fluticasone propionate BID or equipotent ICS daily dosage to a maximum of 2000 mcg/day of fluticasone propionate or clinically comparable) in combination with a LABA as second controller for at least 3 months with a stable dose  $\geq 1$  month prior to Visit 1. Please note that the lower limit of allowed ICS dose (500 mcg of fluticasone propionate daily) corresponds to upper limit of medium dose defined by GINA guidelines. Patients receiving medium ICS dose  $< 500$  mcg daily are not eligible.
- I 03. Patients with prebronchodilator forced expiratory volume (FEV1)  $> 40\%$  of predicted normal at Visit 1/Screening. Prebronchodilator FEV1  $\geq 50\%$  but  $\leq 85\%$  of predicted normal at Visit 2/Baseline.
- I 04. Patients with reversibility of at least 12% and 200 mL in FEV1 after administration of 2 to 4 puffs (200-400 mcg) of albuterol/salbutamol or levalbuterol/levosalbutamol during screening or documented history of a reversibility test that meets this criteria within 12 months prior to Visit 1 or documented positive response to methacholine challenge (a decrease in FEV by 20% [PC20] of  $< 8\text{mg/mL}$ ) within 12 months prior to Visit 1/Screening is considered acceptable to meet this inclusion criterion.
- I 05. Patients must have experienced, within 1 year prior to Visit 1, any of the following events at least once:
  - Treatment with a systemic steroid (oral or parenteral) for worsening asthma.
  - Hospitalization or emergency medical care visit for worsening asthma.
- I 06. Signed written informed consent.

## 7.2 EXCLUSION CRITERIA

Patients who have met all the above inclusion criteria listed in [Section 7.1](#) will be screened for the following exclusion criteria which are sorted and numbered in the following 3 subsections:

### 7.2.1 Exclusion criteria related to study methodology

- E 01. Patients less than 18 years or  $>70$  years of age (ie, have reached the age of 71 at the screening visit).
- E 02. Patients with body mass index (BMI)  $<16$ .
- E 03. Chronic lung disease (for example, chronic obstructive pulmonary disease [COPD], or idiopathic pulmonary fibrosis [IPF]), which may impair lung function, or another diagnosed pulmonary or systemic disease associated with elevated peripheral eosinophil counts, for eg eosinophilic granulomatosis with polyangiitis.
- E 04. History of life threatening asthma (ie, severe exacerbation that requires intubation).
- E 05. Co-morbid disease that might interfere with the evaluation of IMP.
- E 06. Patients with any of the following events within the 4 weeks prior to their Screening Visit 1 or during the screening period:
  - Treatment with 1 or more systemic steroid (oral or parenteral) bursts for worsening asthma.
  - Hospitalization or an emergency medical care visit for worsening asthma.
- E 07. Asthma Control Questionnaire 5-question version (ACQ-5) score  $<1.25$  or  $>3.0$  at V2/randomization. During the screening period an ACQ-5 of up to  $\leq 4$  is acceptable.
- E 08. Anti-IgE therapy (eg, omalizumab [Xolair®]) within 130 days prior to Visit 1 or any other biologic therapy (including anti-IL5 mAb) or systemic immunosuppressant (eg, methotrexate, any anti-TNF mAbs, B and/or T cell targeted immunosuppressive therapies) to treat inflammatory disease or autoimmune disease (eg, rheumatoid arthritis, inflammatory bowel disease, primary biliary cirrhosis, systemic lupus erythematosus, multiple sclerosis) and other diseases, within 2 months or 5 half-lives prior to Visit 1, whichever is longer.
- E 09. Patients with a history of a systemic hypersensitivity reaction to a monoclonal antibody.
- E 10. Patients on or initiation of bronchial thermoplasty within 2 years prior to Visit 1 or plan to begin therapy during the screening period or the randomized IMP treatment period.
- E 11. Current smoker or cessation of smoking within the 6 months prior to Visit 1.
- E 12. Previous smoker with a smoking history  $>10$  pack-years.

- E 13. Current history of substance and/or alcohol abuse.
- E 14. Inability to follow the procedures of the study (eg, due to language problems, psychological disorders) or unable to read, understand and fill a questionnaire or use an electronic diary without any help.
- E 15. Exposure to another investigative drug (small molecules as well as monoclonal antibodies) within a time period prior to Visit 1 that is <5 PK half-lives of the antibody. In case the half-life is not known, then the minimum interval since the exposure to the prior investigative antibody is 6 months. The minimum interval since exposure to any other (non-antibody) investigative study medication is 30 days prior to Visit 1.
- E 16. Clinically relevant abnormal laboratory values suggesting an unknown disease and requiring further evaluation.
- E 17. Patients who have previously been treated in any clinical trial of SAR440340 or dupilumab, or have been treated with commercially available dupilumab.
- E 18. Patient is the Investigator, or any Subinvestigator, research assistant, pharmacist, study coordinator, other staff or relative thereof directly involved in the conduct of the study.
- E 19. Prisoners and patients who are legally institutionalized.

#### **7.2.2 Exclusion criteria related to the active comparator and/or mandatory background therapies**

- E 20. Clinically significant abnormal electrocardiogram (ECG) at Visit 1 that may affect the conduct of the study in the judgment of the Investigator.
- E 21. Concomitant severe diseases or diseases for which the use of ICS (eg, active and inactive pulmonary tuberculosis) or LABA based on judgment of Investigator are contraindicated.
- E 22. Use of injectable glucocorticosteroids or oral systemic glucocorticosteroids within 1 month prior to Visit 1/Screening or more than 4 courses of IV glucocorticosteroids within the 6 months prior to Visit 1.
- E 23. Patients during the screening period that require medications or therapy that are prohibited as concomitant medications (see [Section 8.8](#)).
- E 24. A patient with a history of clinically significant renal, hepatic, cardiovascular, metabolic, neurologic, hematologic, ophthalmologic, respiratory, gastrointestinal, cerebrovascular or other significant medical illness or disorder which, in the judgment of the Investigator, could interfere with the study or require treatment that might interfere with the study. Specific examples include but are not limited to uncontrolled diabetes, severe hypertension, severe ischemic heart disease, unstable angina in the last 6 months, unstable cardiac arrhythmias, and Class IV heart failure.
- E 25. Exclusion related to tuberculosis (TB):

- Active TB or a history of incompletely treated TB.
- Confirmed Quantiferon-positive patients (no active disease) are excluded from the study unless all of the following conditions are met:
  - Patients with a history of prior documented completed chemoprophylaxis for latent tuberculosis infection (TBI) (with a treatment regimen as per local guidelines) or treatment of active TBI, and
  - Has obtained consultation with a specialist to rule out or treat active TBI, and
  - Review and approval from Sponsor has been granted.
- Suspected extrapulmonary TB infection.
- Patients at high risk of contracting TB, such as close contact with individuals with active or latent TB.
- Patient who received Bacille Calmette Guerin (BCG)-vaccination within 12 months prior to Screening Visit 1.

E 26. Patients on DPI controller within 1 month prior to visit 1 in those countries where the study specified doses of controllers are not available in the DPI formulation

### **7.2.3 Exclusion criteria related to the current knowledge of SAR440340**

E 27. Known allergy to doxycycline or related compounds or known allergy to SAR440340 excipients.

E 28. Females who are lactating, breastfeeding or who are pregnant.

E 29. Women of childbearing potential (premenopausal female biologically capable of becoming pregnant) who:

- Do not have:
  - A confirmed negative serum  $\beta$ -human chorionic gonadotropin ( $\beta$ -hCG) test at Visit 1.
  - Negative urine pregnancy test prior to Visit 2/Randomization.
- Who are not protected by one of the acceptable forms of effective contraception (See [Appendix A](#)) during the protocol-defined time frame ([Section 6.2.1](#)).

Postmenopausal women (defined as at least 12 consecutive months without menses) are not required to use additional contraception.

For men in the study:

- Male participants with female partners of childbearing potential are not eligible to participate unless they agree to ONE of the following (during the protocol-defined time frame [[Section 6.2.1](#)]):

- Are abstinent from penile-vaginal intercourse as their usual and preferred lifestyle (abstinent on a long term and persistent basis) and agree to remain abstinent.
- Agree to use a male condom plus partner use of a contraceptive method with a failure rate of <1% per year (see [Appendix A](#)) when having penile-vaginal intercourse with a woman of childbearing potential who is not currently pregnant.
- Men with a pregnant or breastfeeding partner must agree to remain abstinent from penile-vaginal intercourse or use a male condom during each episode of penile penetration (during the protocol-defined time frame [[Section 6.2.1](#)]).

E 30. Diagnosed active parasitic infection (helminthes), suspected or high risk of parasitic infection, unless clinical and (if necessary) laboratory assessments have ruled out active infection before randomization.

E 31. History of human immunodeficiency virus (HIV) infection or positive HIV 1/2 serology at Visit 1.

E 32. Known or suspected history of immunosuppression, including history of invasive opportunistic infections (eg, tuberculosis, histoplasmosis, listeriosis, coccidioidomycosis, pneumocystosis, aspergillosis), despite infection resolution; or unusually frequent, recurrent or prolonged infections, per Investigator's judgment.

E 33. Evidence of acute or chronic infection requiring treatment with antibacterials, antivirals, antifungals, antiparasitics, or antiprotozoals within 4 weeks before Visit 1, significant viral infections within 4 weeks before Visit 1 that may not have received antiviral treatment (eg, influenza receiving only symptomatic treatment).

E 34. Live attenuated vaccinations within 12 weeks prior to Visit 1 or planned live, attenuated vaccinations during the study; see [Appendix B](#) for list of prohibited live, attenuated vaccines.

E 35. Patients with autoimmune disease or patients using systemic immunosuppressive therapy for autoimmune disease (eg, rheumatoid arthritis, inflammatory bowel disease, primary biliary cirrhosis, systemic lupus erythematosus, multiple sclerosis, etc) or patients with high titer autoantibodies at screening who are suspected of having high risk for developing autoimmune disease at the discretion of the Investigator or the Sponsor.

E 36. Patients requiring maintenance treatment with non-selective β-1 adrenergic receptor blockers.

E 37. Active hepatitis or patients with positive or indeterminate hepatitis B surface antigen (HBs Ag), hepatitis B core antibody (HBc Ab) (Confirmed with presence of hepatitis B virus [HBV] deoxyribonucleic acid [DNA]) or positive hepatitis C virus antibody (HCV Ab) (Confirmed with presence of HCV RNA [RNA]) at Screening Visit 1.

E 38. Any prior history of malignancy or active malignancy, including lymphoproliferative diseases (except successfully treated carcinoma in-situ of the cervix, non-metastatic

squamous cell or basal cell carcinoma of the skin) within 5 years prior to Screening Visit 1.

E 39. Clinically significant laboratory tests at Visit 1:

- Alanine transaminase (ALT) or aspartate transaminase (AST)  $>3$  times upper limit of normal range (ULN),
- Hemoglobin  $<10$  g/dL for male and  $<9$  g/dL for female,
- Neutrophils  $<1.5$  K/mm^3 (except  $<1.0$  /mm^3 for those of African descent),
- Platelets  $<100$  K/mm^3,
- Creatinine  $\geq 150$   $\mu$ mol/L.

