Formulation:	SAR440340 for SC administration: 1 vial of lyophilisate drug product (287 mg) is reconstituted with 2.5 mL of sterile water for injection resulting in 2.9 mL of 100 mg/mL SAR440340 DP. A volume of 1.5 mL per injection will be withdrawn from the vial. Sterile placebo will be provided in matched glass vials. Dupilumab for SC administration is supplied as 150 mg/mL in glass prefilled syringes to deliver 300 mg in 2.0 mL. Placebo matching dupilumab is prepared in the same formulation as dupilumab, without the addition of protein.

Route of administration:	SC. All IMP applications will be done as separate injections.
Dose regimen:	
SAR440340 (300 mg) administered as 2 SC injections q2w for 12 weeks and coadministration of dupilumab placebo as 1 SC injection q2w for 12 weeks
 
Dupilumab (300 mg) administered as 1 SC injection q2w for 12 weeks and coadministration of SAR440340 placebo as 2 SC injections q2w for 12 weeks
 
SAR440340 (300 mg) administered as 2 SC injections q2w for 12 weeks and coadministration of dupilumab (300 mg) administered as 1 SC injection q2w for 12 weeks
 
Coadministration of matching placebos for SAR440340 and dupilumab administered as 2 and 1 SC injections, respectively, q2w for 12 weeks

Noninvestigational medicinal products	Background Therapy

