2 puffs of 125/25 mcg (250/50 mcg) BID or  
2 puffs of 250/25 mcg (500/50 mcg) BID

Please note that patients should use the same inhaler type (either DPI or MDI) throughout the study.

Patients who satisfy the inclusion and exclusion criteria will be randomized (1:1:1:1 ratio) to one of the following treatment groups:

- SAR440340 (300 mg) administered as 2 SC injections q2w for 12 weeks and coadministration of dupilumab placebo as 1 SC injection q2w for 12 weeks.
- Dupilumab (300 mg) administered as 1 SC injection q2w for 12 weeks and coadministration of SAR440340 placebo as 2 SC injections q2w for 12 weeks.
- SAR440340 (300 mg) administered as 2 SC injections q2w for 12 weeks and coadministration of dupilumab (300 mg) administered as 1 SC injection q2w for 12 weeks.
- Coadministration of matching placebos for SAR440340 and dupilumab administered as 2 and 1 SC injections, respectively, q2w for 12 weeks.

Visits during the 12-week IMP treatment period will occur every week and will be followed by a 20-week observational follow-up period.

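### E 27 excludes known allergy to SAR440340 excipients but does not name dupilumab excipients, although every arm is injected with the dupilumab formulation

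*Protocol*

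**What the plan says.** The only excipient-allergy criterion is E 27 in Protocol Section 7.2.3: "Known allergy to doxycycline or related compounds or known allergy to SAR440340 excipients". That subsection is headed "Exclusion criteria related to the current knowledge of SAR440340", so its scope is one of the two investigational products. The preceding subsection, 7.2.2, is headed "Exclusion criteria related to the active comparator and/or mandatory background therapies" and contains no allergy item.

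On what is injected, the Clinical Trial Summary states: "Placebo matching dupilumab is prepared in the same formulation as dupilumab, without the addition of protein". Section 6.1 gives each arm a dupilumab-type injection. The SAR440340 arm has "coadministration of dupilumab placebo as 1 SC injection q2w for 12 weeks", and the double-placebo arm has "Coadministration of matching placebos for SAR440340 and dupilumab administered as 2 and 1 SC injections, respectively, q2w for 12 weeks". The other two arms receive active dupilumab on the same schedule.

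The amendment 01 summary says that the reference to SAR440340 excipients in E 27 was added as a clarification. Its rationale for E 09, on past reactions to monoclonal antibodies, considers hypersensitivity to both investigational products. No reason is given for naming the excipients of only one of them.

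**The concern.** The protocol accepts that a known excipient allergy is a reason not to inject a patient, and it treats hypersensitivity as a real risk: Section 10.6.1 sets out observation after dosing, readiness to treat anaphylaxis, and reporting rules. Yet the explicit screen covers one of two products that every patient receives. Read literally, it does not stop a patient with a known allergy to a dupilumab-only excipient from being randomized and exposed to that excipient, whichever arm is drawn. What is at stake is an avoidable reaction in such a patient. The primary endpoint, the power and the treatment comparison are not at stake.

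**Working it through.** The plan states no figure on this point, so the check is mainly a reading of the text.

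**Step 1: who receives the dupilumab formulation.** From Section 6.1 (regimens) and the Clinical Trial Summary (60 patients per arm, composition of the placebo):

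| Arm | Dupilumab-type injection | Planned patients | Dupilumab excipients received |
|---|---|---|---|
| SAR440340 | "coadministration of dupilumab placebo as 1 SC injection q2w for 12 weeks" | 60 | yes, by placebo |
| Dupilumab | "Dupilumab (300 mg) administered as 1 SC injection q2w for 12 weeks" | 60 | yes, by active syringe |
| Coadministration | "coadministration of dupilumab (300 mg) administered as 1 SC injection q2w for 12 weeks" | 60 | yes, by active syringe |
| Placebo | one matching placebo injection q2w | 60 | yes, by placebo |

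Exposed: 4 × 60 = 240 of about 240 planned patients, 120 by active syringe and 120 by placebo.

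**Step 2: how often.** The visit-by-visit procedures in Section 10.1.2 place IMP administration at Weeks 0, 2, 4, 6, 8 and 10. That is 6 injections of the dupilumab formulation per completer, and at most 240 × 6 = 1,440 in the trial. Patients who stop early receive fewer.

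**Step 3: which criteria could exclude a known allergy to a dupilumab excipient.** Reading E 01 to E 41:

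- E 27 names doxycycline and related compounds, and SAR440340 excipients. It reaches a dupilumab excipient only if SAR440340 contains it too.
- E 09 needs a past systemic reaction to a monoclonal antibody. It does not ask whether protein or excipient was the cause, so it catches some relevant patients, but not those whose allergy came to light with another kind of product.
- E 17 removes anyone already treated with dupilumab, including anyone who reacted to it. It leaves dupilumab-naive patients.
- E 20 to E 26, in the subsection that includes the active comparator, cover ECG, contraindications to ICS or LABA, corticosteroid use, prohibited medication, significant illness, tuberculosis and inhaler availability. None concerns allergy.
- E 05 and E 24 are general. E 24 turns expressly on investigator judgment, and E 05 leaves open what counts as interfering comorbidity. Neither mentions allergy or excipients.

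Criteria that explicitly exclude a known allergy to a dupilumab excipient: 0 of 41.

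**Step 4: who is left.** The gap is confined to patients who meet all of these conditions: dupilumab-naive; no past systemic reaction to a monoclonal antibody; a known allergy to an ingredient of the dupilumab formulation; and that ingredient absent from SAR440340. The documents list the excipients of neither product and give no prevalence, so this group cannot be counted from them.

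**Step 5: weight of one event.** With 60 per arm, one reaction is 1/60 = 1.7 percentage points of an arm's rate. This is true of any single event and is not an estimate of the effect.

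**The case against.** The case against rests on how narrow the gap is. Excipient overlap may close it altogether: if every dupilumab excipient is also in SAR440340, E 27 already does the work. E 09 and E 17 remove part of the group, an investigator may exclude the rest under E 05 or E 24, and the Section 10.6.1 safeguards (at least 30 minutes of observation, with trained staff and medication at hand) apply to everyone. E 27 is also consistent with the heading it sits under, so nothing contradicts it; a criterion is absent.

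Most of this stands as a limit on size. It does not explain why SAR440340 excipients needed an explicit criterion and dupilumab excipients did not. Observation limits the harm of a reaction but does not prevent one, and Section 10.6.1 itself notes that reactions may begin within a few hours and that late-phase reactions may appear at 10 to 12 hours.

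Three stronger readings are tempting, and the documents do not support them:

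- A reader might infer that a patient allergic to a dupilumab excipient is certainly eligible and would be dosed. The overlap is unknown and E 05 and E 24 leave room for exclusion, so the text shows only that no criterion explicitly requires exclusion.
- A reader might infer that excipient reactions would distort the control arm. All four arms receive the same dupilumab excipients and are randomized, so the expected risk is equal; rare events would add noise, not bias.
- A reader might infer that any such reaction becomes an AESI and ends treatment. Under Section 10.4.1.3 a hypersensitivity AESI is an anaphylactic reaction or a systemic allergic reaction that requires treatment. Under Sections 10.3.3 and 10.6.1, permanent discontinuation on that ground also requires a relation to IMP. Milder reactions meet neither rule.

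**Conclusion.** The point holds as a gap in eligibility wording that bears on patient safety. E 27 covers the excipients of one of two products injected in all four arms, and no other criterion explicitly covers those of the other. The exposure is universal (about 240 patients, up to six visits each), but the patients for whom it matters are probably very few, and there are none if the dupilumab excipients are all contained in SAR440340. That overlap is the main assumption, and it cannot be settled from the protocol or SAP. There is no effect on sample size, significance level, primary endpoint or analysis model, and no expected bias between arms. This is a cheap improvement.

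**What to change.** Reconcile E 27 with the product descriptions in the Clinical Trial Summary and the regimens in Section 6.1, in one of two ways:

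1. Extend E 27 to known allergy to excipients of any investigational product or matching placebo.
2. If the SAR440340 excipients already include every dupilumab excipient, document that, so that the present wording is seen to be sufficient.

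The first option costs one phrase in a protocol amendment, one line on the screening checklist, and at most a very few extra screen failures. The second costs a comparison of the two formulations and a sentence recording the result. Neither needs a change to the SAP.

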## **8.4 METHOD OF ASSIGNING PATIENTS TO TREATMENT GROUP**

Randomized treatment kit number lists will be generated centrally by Sanofi. The investigational product (SAR440340 or matching placebo and dupilumab or matching placebo) will be packaged in accordance with these lists. The Sanofi clinical supplies team will provide the randomized

treatment kit number lists and the randomization scheme to the centralized treatment allocation system (IVRS/IWRS). This centralized treatment allocation system will generate the patient randomization list according to which it will allocate the treatment to the patients. Patients who meet the entry criteria will be randomized to receive either SAR440340 or matching placebo in combination with either dupilumab or matching placebo. The Investigator obtains treatment kit numbers at randomization and subsequent scheduled visits via an IVRS/IWRS that will be available 24 hours a day. Patients will be randomized in a 1:1:1:1 ratio to receive SC administrations of either:

- SAR440340 300 mg q2w, and coadministration of dupilumab placebo or
- Dupilumab 300 mg q2w and coadministration of SAR440340 placebo or
- SAR440340 300 mg and dupilumab 300 mg q2w coadministration or
- Placebo to both SAR440340 and dupilumab q2w coadministration.

If certain dynamic laboratory tests do not meet the eligibility criteria, these laboratory assessments may be repeated, at the discretion of the Investigator, if it is judged to be likely to return to acceptable range for study inclusion within the screening visit window (28 days) prior to Day 1. These patients do not need to sign a new informed consent form (ICF) and be allocated a new patient number within this same screening window.

Patients who meet exclusion criteria may be rescreened once during the open screening period of the study; a different patient identification number will be issued. Re-screening is not permitted if the patient fails to meet inclusion criteria. There is no requirement for a waiting period between the screen-failure date and the rescreening date. The IVRS/IWRS report will flag rescreened patients. Patients that are rescreened must sign a new ICF and all Visit 1 procedures must be repeated.

Randomization will be stratified by Screening Visit 1 eosinophil count and by country.

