#### **9.2.3.4 Clinical laboratory tests**

The clinical laboratory tests will be conducted by an accredited (College of American Pathologists or equivalent) central laboratory with national and regional clinical licenses as required for diagnostic testing and must provide evidence of participation in proficiency testing, as appropriate. After reviewing the laboratory report and evaluating any results that are outside the normal range, the Investigator must sign and date the laboratory report.

Abnormal laboratory values that are considered to be clinically significant by the Investigator must be repeated as soon as possible after receiving the laboratory report to rule out laboratory error. Persistent abnormal laboratory values should be repeated until they return to normal or until an etiology of the persistent abnormality is determined.

Refer to [Section 1.2](#) for the description of the clinical laboratory evaluations and the schedule of laboratory evaluations performed throughout this study.

The clinical laboratory parameters that will be measured are:

- Hematology: To include hemoglobin, hematocrit, platelet count, total white blood cell (WBC) count with 5-part differential count, and total red blood cell (RBC) count. Neutrophil and eosinophil counts (study biomarkers) will also be evaluated as a part of hematology testing.
- Serum chemistry: To include creatinine, blood urea nitrogen, glucose, uric acid, total cholesterol, total protein, albumin, total bilirubin (in case of values above the normal range, differentiation in conjugated and nonconjugated bilirubin), alanine aminotransferase (ALT), aspartate aminotransferase (AST), alkaline phosphatase, electrolytes (sodium, potassium, chloride), bicarbonate, and creatine phosphokinase (CPK).
- Urinalysis will include specific gravity, pH, glucose, ketones, blood, protein, nitrate, leukocyte esterase, urobilinogen, and bilirubin. If any parameter on the dipstick is abnormal, a urine sample should be sent to the central laboratory for quantitative measurement. If positive for protein and/or red blood cells, microscopic analysis will be performed by the central laboratory.

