#### **10.4.6 Guidelines for management of specific laboratory abnormalities**

Decision trees for the management of certain laboratory abnormalities by Sanofi are provided in [Appendix H](#).

The following laboratory abnormalities should be monitored, documented, and managed according to the related flow chart in protocol appendices.

- Neutropenia
- Thrombocytopenia
- Increase in ALT
- Increase in serum creatinine
- Increase in CPK

Note: In some clinical trials these laboratory abnormalities can be considered as AESIs. For this study, only significant ALT increase will be considered as AESIs (see [Section 10.4.1.3](#))

In addition, on treatment eosinophil counts  $>3000/\text{mm}^3$  (3.0 giga/L) (confirmed by retest) are to be reported as AEs.

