**Note:**

- The procedures described in the above flowchart are to be discussed with the patient only in case the event occurs. If applicable (according to local regulations), an additional consent (e.g., for HIV testing) will only be obtained in the case the event actually occurs.
- For individuals of African descent, the relevant value of concern is <1000/mm^3

Neutropenia is to be recorded as an AE only if at least 1 of the criteria listed in the general guidelines for reporting AEs in [Section 10.4.3](#) is met.

[figure not shown]

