eGFR (mL/min/1.73m ²) (Estimate of GFR based on an MDRD equation)	<15 (end stage renal disease) ≥15 - <30 (severe decrease in GFR) ≥30 - < 60 (moderate decrease in GFR) ≥60 - <90 (mild decrease in GFR) ≥ 90 (normal GFR)	FDA draft Guidance 2010 Pharmacokinetics in patients with impaired renal function-study design, data analysis, and impact on dosing and labeling
Creatinine	≥150 µmol/L (Adults) ≥30% change from baseline ≥100% change from baseline	Benichou C., 1994.
Uric Acid		Harrison- Principles of internal Medicine 17 th Ed., 2008.
Hyperuricemia	>408 µmol/L	
Hypouricemia	<120 µmol/L	
Blood Urea Nitrogen	≥17 mmol/L	
Chloride	<80 mmol/L ≥115 mmol/L	
Sodium	≤129 mmol/L ≥160 mmol/L	
Potassium	<3 mmol/L ≥5.5 mmol/L	FDA Feb 2005.
Total Cholesterol	≥7.74 mmol/L	Threshold for therapeutic intervention.
Triglycerides	≥4.6 mmol/L	Threshold for therapeutic intervention.
Lipasemia	≥3 ULN	
Amylasemia	≥3 ULN	

**CRITERIA for POTENTIALLY CLINICALLY SIGNIFICANT ABNORMALITIES
for phase 2/3 studies (oncology excepted)**

*(From BTD-009536 "Analysis and reporting of safety data from clinical trials through the Clinical Study Report"
Version 3, 21-MAY-2014)*

Parameter	PCSA	Comments
Glucose		
Hypoglycaemia	≤ 3.9 mmol/L and $< LLN$	ADA May 2005.
Hyperglycaemia	≥ 11.1 mmol/L (unfasted); ≥ 7 mmol/L (fasted)	ADA Jan 2008.
HbA1c	$> 8\%$	
Albumin	≤ 25 g/L	
CRP	> 2 ULN or > 10 mg/L (if ULN not provided)	FDA Sept 2005.
Hematology		
WBC	< 3.0 Giga/L (Non-Black); < 2.0 Giga/L (Black) ≥ 16.0 Giga/L	Increase in WBC: not relevant. To be interpreted only if no differential count available.
Lymphocytes	> 4.0 Giga/L	
Neutrophils	< 1.5 Giga/L (Non-Black); < 1.0 Giga/L (Black)	International Consensus meeting on drug-induced blood cytopenias, 1991. FDA criteria.
Monocytes	> 0.7 Giga/L	
Basophils	> 0.1 Giga/L	
Eosinophils	> 0.5 Giga/L or $> ULN$ (if $ULN \geq 0.5$ Giga/L)	Harrison- Principles of internal Medicine 17 th Ed., 2008.
Hemoglobin	≤ 115 g/L (Male); ≤ 95 g/L (Female) ≥ 185 g/L (Male); ≥ 165 g/L (Female) Decrease from Baseline ≥ 20 g/L	Criteria based upon decrease from baseline are more relevant than based on absolute value. Other categories for decrease from baseline can be used (≥ 30 g/L, ≥ 40 g/L, ≥ 50 g/L).
Hematocrit	≤ 0.37 v/v (Male) ; ≤ 0.32 v/v (Female) ≥ 0.55 v/v (Male) ; ≥ 0.5 v/v (Female)	
RBC	≥ 6 Tera/L	Unless specifically required for particular drug development, the analysis is redundant with that of Hb. Otherwise, consider FDA criteria.

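### Exclusion criterion E 39 prints the neutrophil limit for patients of African descent without the K, so the printed figure is 1000 times below the evident intended limit of 1000/mm³

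*Protocol*

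**What the plan says.** Criterion E 39 (Protocol Section 7.2.3) lists five laboratory exclusions at Visit 1: transaminases, hemoglobin, neutrophils, platelets and creatinine. The neutrophil item reads "Neutrophils $<1.5$ K/mm 3 (except $<1.0$ /mm 3 for those of African descent". The platelet item on the next line is below 100 K/mm³, again with the K.

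The neutrophil threshold for this group appears in two other places:

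- The neutropenia note in Protocol Appendix H says "For individuals of African descent, the relevant value of concern is" below 1000/mm³.
- The hematology part of SAP Appendix A flags neutrophils below 1.5 Giga/L in non-Black patients and below "1.0 Giga/L (Black") in Black patients.

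E 39 is current text, and the amendment summary has no entry for it.

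**The concern.** In this protocol, mm³ without a K means whole cells. The eosinophil strata are cut at 150 and 300/mm³, and Section 10.4.6 equates an eosinophil count of 3000/mm³ with 3.0 giga/L. On that convention the E 39 exception is a limit of one neutrophil per mm³.

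E 39 is a numeric safety criterion. Followed as printed, it keeps the neutropenia exclusion for everyone else and in effect removes it for patients of African descent. Protocol Section 4.5 names a theoretical infection risk from blocking host-defense pathways with the combination, and Section 10.6.3 requires monitoring for infection, so the limit is not idle.

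The limit also governs screening retests. Section 8.4 says: "If certain dynamic laboratory tests do not meet the eligibility criteria, these laboratory assessments may be repeated". A site needs the right limit to know whether a retest is called for and whether the repeat value passes. Section 10.3.1 also makes restarting treatment after a temporary stop depend on the selection criteria still being met, and refers back to Section 7.2. Because E 39 is worded for Visit 1, its use at restart is arguable.

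**Working it through.** This is a unit check. No power or sample size formula applies.

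**Inputs**

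- E 39, general limit: 1.5 K/mm³.
- E 39, exception as printed: 1.0/mm³.
- Protocol Appendix H, African descent: 1000/mm³.
- SAP Appendix A: 1.5 Giga/L (non-Black) and 1.0 Giga/L (Black).
- Protocol Section 10.4.6: the eosinophil reporting threshold of 3000/mm³ is given in parentheses as "3.0 giga/L) (confirmed by retest) are to be reported as AEs".

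**Conversion**

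From Section 10.4.6, 3000/mm³ = 3.0 giga/L, so 1/mm³ = 3.0/3000 = 0.001 giga/L. From first principles, 1 giga/L = 10⁹/L and 1 L = 10⁶ mm³, so 1 giga/L = 10⁹/10⁶ = 1000/mm³ = 1 K/mm³. The two agree.

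**Results**

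| Limit | Cells/mm³ | Giga/L |
|---|---|---|
| E 39, general | 1500 | 1.5 |
| SAP, non-Black | 1500 | 1.5 |
| E 39, exception as printed | 1 | 0.001 |
| E 39, exception with the K | 1000 | 1.0 |
| Protocol Appendix H, African descent | 1000 | 1.0 |
| SAP, Black | 1000 | 1.0 |

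- The general E 39 limit agrees with the SAP. The printed exception agrees with neither Appendix H nor the SAP.
- Intended over printed: 1000/1 = 1000.
- General limit over exception: 1500/1 = 1500 as printed, and 1500/1000 = 1.5 with the K restored. The SAP ratio is 1.5/1.0 = 1.5.

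Restoring the K therefore reproduces both other sources exactly.

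**The case against.** The strongest reply is that this is an editorial slip that corrects itself. The exception sits in parentheses after a limit given in K/mm³, so a reader carries the unit over, and one neutrophil per mm³ is too absurd to be applied. Nothing has been miscalculated, and no analysis changes.

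Other text also limits the consequence:

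- E 16 excludes patients with "Clinically relevant abnormal laboratory values suggesting an unknown disease and requiring further evaluation".
- E 24 covers a history of significant hematologic illness, and E 32 covers suspected immunosuppression.
- Section 9.2.3.4 requires that "After reviewing the laboratory report and evaluating any results that are outside the normal range, the Investigator must sign and date the laboratory report".
- For neutropenia that arises on treatment, Section 10.4.6 says "The following laboratory abnormalities should be monitored, documented, and managed according to the related flow chart in protocol appendices", and Appendix H carries the right number.

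Finally, the K could have been lost when the PDF was read. Small character anomalies occur elsewhere in the text, such as a heading that prints RQLO(S) for RQLQ(S) in SAP Section 2.1.3.2.5.

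Much of this stands. The practical risk is small, and an extraction loss cannot be excluded, although the K was read correctly earlier on the same line and again on the next. What does not follow is that the text can be left alone. The screening safeguards rest on judgement, and Appendix H governs follow-up rather than entry, so none of them replaces the numeric limit. An objective eligibility limit should not depend on each reader silently correcting it.

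**Conclusion.** The point holds. As it reads in the document, the E 39 exception is 1 cell/mm³ (0.001 giga/L) where 1000/mm³ (1.0 giga/L) is evidently meant, a factor of 1000. It affects one of five laboratory items, in one subgroup, at one stated time point. The documents do not give the number of patients concerned, and nothing in them suggests that the limit was misapplied. Sample size, power, the efficacy analyses and the other E 39 limits are untouched.

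The conclusion rests on two assumptions: that the extracted text matches the printed page, and that Appendix H and the SAP state the intended threshold. The second is well supported, because the two sources agree with each other and with the structure of the E 39 line.

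**What to change.** Change the exception in E 39 to below 1.0 K/mm³ for those of African descent, by clarification letter or in the next amendment. First check the original page, in case the K is already there. Confirm with sites that eligibility at Visit 1, including any screening retest, is judged at 1000/mm³ for this group. The cost is one letter in one criterion and one confirmation. The SAP, the sample size and data collection do not change.
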